### Participant Compensation

Aim 1: Upon enrollment, participants will be reimbursed with a \$50 gift card for completing baseline assessments via REDCap and master's level administered PTSD Diagnostic Interview (see Table 2). Participants will receive \$50 for completion of post-intervention assessments and \$25 for completion of a 20-minute exit interview after completion of CPT sessions. Participants will also receive \$5 per photo they submit of their prescription bottle and refill (i.e., self-reported adherence; totaling \$15 per participant). Participants will be paid up to \$140 for participation in Aim 1 of the study.

Aim 2: Upon enrollment, all participants will be reimbursed with a \$50 gift card for completing baseline assessments at the PTSD Diagnostic Interview. Participants assigned to the intervention group will receive \$40 for attending the first session, then \$60 for post-intervention assessments and 20-minute exit interview after completion of CPT-L sessions (i.e., post intervention ~6 weeks after study enrollment); and a \$75 gift card for 3 month follow up surveys collected online or in person (CAPS can be conducted via telehealth by project coordinator). Participants enrolled in the control group will receive \$50 for completing the first set of assessments, PTSD Diagnostic Interview, and for enrolling in the study, and then \$40 for completing the Lifesteps session. Then, they will receive \$60 for post-intervention assessments and 20-minute exit interview after completion of CPT-L sessions (i.e., post intervention ~6 weeks after study enrollment); and a \$75 gift card for 3 month follow up surveys. Participants will also receive up to \$15 for self-reported adherence photos. Thus, participants can be paid up to \$240 for participation in Aim 2.

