In Aim 2, steps 7-8 of ADAPT-ITT will be completed. The project therapist is trained in evidence-based PTSD treatment, including CPT, thus Training in the integrated CPT-L protocol (step 7) will be relevant for adherence and stigma adaptations. For Testing the adapted intervention (step 8), we will randomize **60 adults** aged 18+ who meet DSM 5 criteria for PTSD and present for treatment at MUSC, Roper Ryan White Clinic, or other HIV care clinic, to either CPT-L + standard of care (SOC) or Lifesteps only + SOC. Participants must have experienced at least one traumatic event and report current clinically significant PTSD symptoms (via CAPS clinical interview). Participants randomized to experimental condition (CPT-L; N=30) will be assigned to the project therapist (trained and supervised in CPT-L). Participants randomized to control condition will receive the unadapted Lifesteps session as well as SOC (measured via chart review), which includes supportive services typically received by PLWH identified as suffering from PTSD. Assessments will be conducted at pre- and post-treatment, and 3-month post study-entry. Outcomes for efficacy testing in the subsequent R01 will be collected, including viral load, ART adherence, clinic attendance, PTSD diagnosis and symptoms, avoidant coping, substance use, and depression.

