**Assessments and Data Collection Procedures.** The PC (blind to condition) will conduct the initial eligibility (baseline) diagnostic assessments and all study assessments. The CAPS will be audio-taped and study personnel will listen to a randomly selected 20% to ensure reliability of CAPS diagnosis over the course of the study. The PC will administer the battery in the HIV care clinic or remotely by phone to the participant, based on participant preference. All timepoints will be collected on all participants, even if they drop out of treatment. Pilot trials indicate that major assessments take between 1.5 – 2 hours to complete. Individuals will be given \$50 for completing the baseline interview, \$40 for attending the first session, then \$60 for post-intervention assessments and 20-minute exit interview after completion of CPT-L sessions (i.e., post intervention ~6 weeks after study enrollment); and a \$75 gift card for 3 month follow up surveys. Several questionnaires were drawn from the PROMIS common data elements and NIH sponsored repositories to promote data sharing (e.g., PROMIS depression and BRICS Social Determinants of Health). Participants will complete a brief electronic diary on a weekly basis to assess use of resources/additional supports. Research has demonstrated the validity of this approach, including capturing “real-time” data beyond what can be captured with retrospective reports. Surveys (<1 minute each) will be electronically collected once a week for the 6 weeks of the intervention period starting one week after randomization (i.e., 6 electronic survey entries), leading up to the 3-month follow up. With input from the CAB, we have established procedures to auto-send an email or SMS text (participant choice) on a set schedule. SMS text messaging is possible via Twilio, embedded within our REDCap system, which allows participants to complete a survey directly from their phone, without having to access a webpage. Participants will be asked permission for the study team to access electronic medical records to collect CD4 count and viral load at the time of enrollment. As an attending physician in the clinic, Co-I [name] is familiar with these electronic records and will oversee the data pull. CD4 T-cell counts and HIV viral load will be measured as standard clinical practice using standard clinical assays (HIV viral load less than 200 considered virologic suppression). Relevant data from the clinic’s electronic medical record (e.g., CD4 count, no-shows) will be collected at intervals and study completion (i.e., 6 months after participation) to document retention in HIV clinical care using the industry standard of 2 appointments with a provider with prescribing privileges per year, no longer than 6 months apart. PI [name] has planned for adequate staff training and coverage based on experience. The PI will assist in training research staff on consent, diagnostic interview, assessment measures, and medical chart data retrieval (with Co-I [name] and Co-I [name] for service utilization data) and will conduct weekly meetings, quarterly reviews, and booster trainings to ensure standardized procedures. See Table 2 for research instruments.

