CAPS PTSD Diagnostic Interview	PC	x	x	x		A 30-item structured clinical interview to derive PTSD diagnoses, but also provides PTSD intensity scores. Considered the gold standard in PTSD assessment and corresponds to DSM-5 criteria for PTSD. Interview items focus on symptom presence, onset and duration of symptoms, subjective distress, impact of symptoms on social and occupational functioning and improvement in symptoms
Life Events Checklist (LEC-5)	P	x		x		Assesses exposure to 16 events known to potentially result in PTSD and includes one additional item assessing any other extraordinarily stressful event not captured in the first 16 items.
PTSD Checklist (PCL)	P	x	x	x	x	Corresponds to current DSM-5 PTSD criteria; 20-items scored on a 0-4 Likert scale for each symptom corresponding to "Not at all" to "Extremely". Psychometric data demonstrates good internal consistency ( $\alpha = .96$ ) and test-retest reliability ( $r = .84$ ).
Emotion Regulation Questionnaire (ERQ)	P	x	x	x		Consists of 10 items capturing two emotion regulation strategies, cognitive reappraisal and emotion suppression on a 7-point Likert scale ("1" strongly disagree, "4" neutral, and "7" strongly agree).
Substance use: AUDIT; DAST	P	x	x	x		Each self report consists of 10 items; excellent reliability and convergent validity.
PROMIS Depression A-6 items	P	x	x	x		Assesses negative mood (e.g., sadness, guilt), views of self (self-criticism), social cognition (loneliness), decreased positive affect and decreased engagement (loss of interest, meaning).
Patient Health Questionnaire (PHQ-9)	P	x	x	x		Validated for use to monitor the severity of depression and response to treatment; scores major depressive episode criteria as "0" (not at all) to "3" (nearly every day).
Participant Treatment Engagement						
Treatment Expectancy Scale	P				x (first wk.)	6-item scale assesses patient expectancy for the intervention to improve their lifestyle/functioning.
Credibility Expectancy Quest.	P	x				Assesses how much participant believes that the intervention will reduce their mental health symptoms.
Engagement in Session	CM				x	Research clinician rates on a 1 to 5 scale on total patient engagement, cooperation.
Services Tracking Form	P	x	x	x	x	6 items (McLellan et al., 1992)  ; records type and amount of services engaged in for PTSD symptoms, including mode (group, individual couples, family, self-help, medication) and # of hours in each service.

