Exit Interview	PC		x			Conducted with PC to avoid potential impression management bias. "what are advantages/ disadvantages of getting referred to PTSD treatment, do family members support you, barriers to participation, are there steps in place to help with participation, what were previous barriers to PTSD treatment; would you recommend this to others; how can this intervention better fit your needs, etc."
Summative Exit Interview	AP		x			A research team member will guide CAB members to understand their reactions to the training and treatment models, perceived fit and usefulness within HIV care clinic treatment settings, identified implementation barriers/facilitators, and recommendations to improve larger scale trial procedures

Note. Res = Respondent; P = Participant; CM = Case Manager; PC = Project Coordinator; AP = Advisory Panel; BL = Baseline

\* Collected in Aim 2 participants

† Adherence will be collected up to 6 months after participant completion

**Impact and Future Directions.** Evaluating evidence-based trauma treatments to target specific needs of hard-to-engage populations will significantly impact public health by improving patient outcomes, engagement, and medication adherence across pathologies and health promotion efforts. This study will provide valuable data for PLWH by establishing the protocol for increasing ART adherence and retention in care through an adapted PTSD treatment, CPT-L.

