
Data Analysis Aim 2. Descriptive analyses will characterize the entire sample and two conditions as appropriate using measures of central tendency or frequency distributions and proportions. Feasibility will be determined by patient willingness to be screened, proportion of participants meeting PTSD criteria, and flow of participants through the study. Feasibility of assessments will be examined through self-report and medical record abstraction. While CPT has been evaluated in other populations, acceptability within PLWH is important for feasibility data. Intervention feasibility will be monitored through randomization, session attendance and quality assurance data collection on intervention fidelity and supervision. Exit interviews will be analyzed using the same techniques for qualitative analyses described for Aim 1. Study feasibility will be determined by ability to adequately randomize and retain study participants throughout study intervention and follow-up, determined through ability to successfully randomize 4+ patients per month and retain 90% of randomized patients throughout the study. In addition to retention, a low rate of missing primary outcome data ( $\leq 10\%$  missing) will demonstrate ability to integrate the intervention with standard clinical care components and medical health records. Protocol adherence will be monitored weekly and reported as the proportion of weekly PCL checklists completed, and distribution of clinician rated treatment engagement and cooperation levels. Acceptable protocol adherence will be determined by completion of  $\geq 80\%$  of assigned weekly PCL checklists across participants.

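### The coordinator described as blind also holds the exit interview about the intervention, so the same person's 3-month CAPS ratings cannot be assumed blind

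*Combined protocol and SAP*

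**What the plan says.** **Blinding.** Section 10.0, Assessments and Data Collection Procedures: "The PC (blind to condition) will conduct the initial eligibility (baseline) diagnostic assessments and all study assessments". Randomization Procedures, in the same section, is softer. It undertakes to try to keep the PC unaware of assignment and, for that reason, has the PI randomise.

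**CAPS.** Table 2 describes the instrument as "A 30-item structured clinical interview to derive PTSD diagnoses, but also provides PTSD intensity scores". It codes the PC against it and marks baseline, Post and 3 months. Section 9.0 also identifies the coordinator as the CAPS assessor, and Participant Compensation (section 5.0) says of the 3-month follow-up that "CAPS can be conducted via telehealth by project coordinator".

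**Exit interview.** Table 2 marks this at Post only, with the entry "Conducted with PC to avoid potential impression management bias". Its sample prompts include "would you recommend this to others; how can this intervention better fit your needs".

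**Arms and timing.** Participant Compensation pays both Aim 2 arms for "post-intervention assessments and 20-minute exit interview after completion of CPT-L sessions (i.e., post intervention ~6 weeks after study enrollment". Section 12.0, Data Analysis Aim 2, adds: "Exit interviews will be analyzed using the same techniques for qualitative analyses described for Aim 1". Section 10.0 sets the schedule: "Assessments will be conducted at pre- and post-treatment, and 3-month post study-entry".

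**The concern.** Participants cannot be blinded, because the PI tells each of them their condition. For a clinician-rated scale such as the CAPS, a rater who does not know the arm is therefore the available protection against detection bias. The plan claims that protection, then gives the rater a task that is likely to undo it before the last rating.

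What is at stake is the between-arm CAPS comparison at 3 months. Aim 2 seeks initial indicators of a PTSD effect at follow-up. Section 12.0 tabulates CAPS estimates by group and visit with Cohen's d, and these are meant to inform the later R01. If the PC has learned the arm by then, readers of those estimates would be relying on a blind that may no longer exist.

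**Working it through.** The plan gives no figure to reproduce. The check sets roles and dates side by side.

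1. **Is it the same person?** Yes. The PC is the CAPS rater (Table 2, section 9.0, Participant Compensation) and the participant exit interviewer (Table 2). No other participant exit interviewer is named. The team member in Table 2's Summative Exit Interview row meets advisory board members, not trial participants.

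2. **Does it apply to both arms of Aim 2?** Yes, by the payment text and the Aim 2 analysis text. The control payment sentence dates the interview by completion of CPT-L sessions, which controls do not receive. I assume that the stated date of about 6 weeks after enrolment applies to them as well.

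3. **Which comes first?** Three months after study entry is about 13 weeks, and Post is at about 6 weeks: 13 − 6 = about 7 weeks between exit interview and 3-month CAPS. If follow-up were counted from the end of treatment, the gap would be longer and the order unchanged.

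4. **Would the interview reveal the arm?** No prompt asks for it. But the interviewee is asked how the intervention could fit better and whether to recommend it. One arm has had a multi-session trauma therapy and the other a single adherence session plus standard care. Disclosure is likely, not certain.

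5. **How many ratings?** The 3-month CAPS of those who gave an exit interview: at most 30 + 30 = 60.

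6. **Is the Post CAPS exposed?** Only if arm-revealing items come before it. The visible text states no order, and the participant flow diagram is not shown.

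7. **Are there other routes to the same rater before the 3-month CAPS?**

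| Route | Where | Condition |
|---|---|---|
| Acceptability survey (usefulness of each session) at Post | Table 2 | If the PC administers it, for example by phone |
| Services Tracking Form (type and hours of PTSD services) | Table 2 | As above |
| Services chart review by the PC | Table 2; section 10.0 | If abstracted before the 3-month CAPS; section 10.0 has record data pulled both at intervals and at study completion |
| Weekly contacts, fidelity-log review, record audits | Section 13.0, B.1 | Assigned to PI or PC; the two correct audit errors together |
| Database checks and discrepant data | Section 13.0, B.3, Data Monitoring | Monitoring by PI or PC; the two resolve discrepancies together |

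8. **Is there a safeguard?** Randomisation by the PI protects the blind only at assignment. The 20% audio review of CAPS interviews addresses reliability, and its listeners are not stated to be blind. I found no second blinded rater, no request that participants withhold their arm, and no rule for handling unblinding.

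9. **Interview time that could be moved:** 60 × 20 min = 1,200 min = 20 hours.

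**The case against.** The best defence has four parts.

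- **This is a feasibility pilot** with a pragmatic sample size, and its efficacy outputs are only initial indicators. That lowers the stakes but does not remove them, because the 3-month CAPS contrast is to be carried into the R01.
- **Only efforts at blinding were promised.** That is true of Randomization Procedures, but the assessment text then states blindness as a fact. The two need reconciling.
- **The PC was chosen on purpose**, to limit impression management. The reason is sound, but any interviewer who does not deliver treatment would serve it equally.
- **PTSD severity is also measured by the PCL**, at each visit and weekly. This stands: the PCL does not depend on a clinician's rating. It gives a second reading of the PTSD effect but does not make the CAPS blind.

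A reader might also infer more than the documents support:

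- *That the CAPS result is biased towards CPT-L.* Nothing in the text gives a direction or size, and unblinding itself is inferred.
- *That the Post CAPS is compromised too.* This depends on an order that the visible text does not give.
- *That the contrast is 18 hours against one session* (12 × 90 min = 1,080 min). Table 1 lists Lifesteps separately and allows variable length beyond 12 sessions, and standard care in either arm may include counselling. Total contact is therefore not fixed.
- *That moving the exit interview alone would restore the blind.* The other routes in the table above would remain.

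**Conclusion.** The point holds for the 3-month CAPS. The plan states that the rater is blind, yet its own assignments have that rater discuss the intervention with participants in both arms beforehand. At most 60 ratings cannot be assumed blind.

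This rests on three assumptions: that the PC conducts the exit interviews as Table 2 says, that control interviews fall at the same Post visit, and that talking about the intervention usually reveals which one was received. The Post CAPS is at risk only conditionally. Other measures that the PC administers or codes, such as appointment attendance, may be affected to a lesser degree. Laboratory values and the feasibility benchmarks are not materially affected. The role conflict is certain on the text; its effect on the estimates cannot be quantified. It should be fixed, because the 3-month CAPS estimates go forward to the next trial and the remedy is cheap.

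**What to change.** 1. **Order and non-disclosure.** At each post-randomisation visit, complete the CAPS first and ask participants not to disclose their condition. This is a wording change.

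2. **Exit interviewer.** Use an existing team member who neither rates the CAPS nor delivers treatment, at a cost of at most 20 hours of interviewing over months 13–30. The documents give no staffing figures, so the sponsor must confirm that such a person is available. If nobody is, hold the interview after the 3-month CAPS. That fallback costs more:
   - Recall is poorer and feedback comes about 7 weeks later.
   - Participants who drop out after Post give no interview, and Aim 2 counts exit-interview findings among its benchmarks. Retention of 80% or 90%, the two targets in the documents, means up to 60 × 0.20 = 12 or 60 × 0.10 = 6 participants lost by study end.
   - The $60 Post payment bundles the interview, so the payment text would have to change.

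3. **Other arm-revealing material.** Until a participant's 3-month CAPS is complete, keep it from the PC. Have the Post Acceptability survey and the Services Tracking Form self-completed in REDCap or given by someone else. Abstract the services chart review afterwards. Assign the weekly contacts, fidelity-log review, record audits and arm-revealing data checks to the PI or another unblinded existing team member. No new visits are needed, but some work moves between staff.

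4. **If these are not adopted in full,** reword section 10.0 to say that blinding of the PC was attempted but is not assured after Post. Report the 3-month CAPS as not reliably blinded, with the PCL beside it.

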
**Table 2. Research Instruments**

Assessment	Res.	BL	Post	3 mon*	weekly	Description
Demographics questionnaire	P	x				Data collected from participant after consent
BRICS NINR Social Determinants of Health	P	x				18-items assess financial resource strain, physical activity, social connectivity/isolation, safety, family income.
MOS Social Support Survey	P	x				19-items assessing different types of support (emotional/informational, tangible, affectionate, and positive social interaction

[[Montreal Cognitive Assessment Test (MoCA)]]	P					[[A brief 10-item screening tool developed to detect cognitive impairment that measures 8 cognitive domains, takes 5-10 minutes to administer (Nesdarnine et al., 2005), and has been tested in PLWH (e.g., Janssen et al., 2015; Koski et al., 2011).]] MoCA-Blind (without requiring visual elements) will be conducted prior to consent as part of the pre-eligibility process.
HIV, Trauma, PTSD, and Related Outcomes from Clinical Interview and Self-Report						
ART adherence (self-report)	P	x	x	x		ACTG trial adherence measure self-report of medication within the last 4 days and self-efficacy.
Saberi Method Adherence	P	x			X (week 4 and week 8)	Another method for ART adherence through collecting self-rated adherence (SRA), Pill count based adherence (PCA), and Proportion of days covered (PDC). PCA and PDC will be collected by the participant sending a text photograph of pharmacy refill and remainder of pills to a MUSC approved study cell phone. SRA, PCA, and PDC will be collected at Baseline, Week 4, and Week 8.
HIV Quality of Life (WHOQOL-BREF)	P	x	x	x		A 26-item measure categorized into four domains (i.e., physical health, psychological well-being, social relationships, and environment); measures effects of disease and health interventions on an individual's perception of quality of life and assesses changes in quality of life across treatment.
HIV stigma measure	P	x	x	x		Developed by Berger et al. (2001)  , revised by Bunn et al. (2007)  ; multiple dimensions of stigma
[[Everyday Discrimination Scale]]	P	x	x	x		[[Developed by Williams et al (1997), 10-item self report measure is a common approach to measuring intersectional stigma (Turan et al. 2019) by asking parallel questions related to different identities.]]
CAPS PTSD Diagnostic Interview	PC	x	x	x		A 30-item structured clinical interview to derive PTSD diagnoses, but also provides PTSD intensity scores. Considered the gold standard in PTSD assessment and corresponds to DSM-5 criteria for PTSD. Interview items focus on symptom presence, onset and duration of symptoms, subjective distress, impact of symptoms on social and occupational functioning and improvement in symptoms
Life Events Checklist (LEC-5)	P	x		x		Assesses exposure to 16 events known to potentially result in PTSD and includes one additional item assessing any other extraordinarily stressful event not captured in the first 16 items.
PTSD Checklist (PCL)	P	x	x	x	x	Corresponds to current DSM-5 PTSD criteria; 20-items scored on a 0-4 Likert scale for each symptom corresponding to "Not at all" to "Extremely". Psychometric data demonstrates good internal consistency ( $\alpha = .96$ ) and test-retest reliability ( $r = .84$ ).
Emotion Regulation Questionnaire (ERQ)	P	x	x	x		Consists of 10 items capturing two emotion regulation strategies, cognitive reappraisal and emotion suppression on a 7-point Likert scale ("1" strongly disagree, "4" neutral, and "7" strongly agree).
Substance use: AUDIT; DAST	P	x	x	x		Each self report consists of 10 items; excellent reliability and convergent validity.
PROMIS Depression A-6 items	P	x	x	x		Assesses negative mood (e.g., sadness, guilt), views of self (self-criticism), social cognition (loneliness), decreased positive affect and decreased engagement (loss of interest, meaning).
Patient Health Questionnaire (PHQ-9)	P	x	x	x		Validated for use to monitor the severity of depression and response to treatment; scores major depressive episode criteria as "0" (not at all) to "3" (nearly every day).
Participant Treatment Engagement						
Treatment Expectancy Scale	P				x (first wk.)	6-item scale assesses patient expectancy for the intervention to improve their lifestyle/functioning.
Credibility Expectancy Quest.	P	x				Assesses how much participant believes that the intervention will reduce their mental health symptoms.
Engagement in Session	CM				x	Research clinician rates on a 1 to 5 scale on total patient engagement, cooperation.
Services Tracking Form	P	x	x	x	x	6 items (McLellan et al., 1992)  ; records type and amount of services engaged in for PTSD symptoms, including mode (group, individual couples, family, self-help, medication) and # of hours in each service.
Support Electronic Survey	P	x	x	x		Captures more ecologically valid data than retrospective recall at three data assessment points (0, post intervention, 3 month follow up), support services will be collected via REDCap survey from baseline until 3 month follow up across both conditions.
Electronic Medical Record Data						
CD4 count	PC	x	x	x		We will use clinic lab test (standard clinical assays) results for our data.
HIV care appointment adherence †	PC	x		x		Electronic medical record data coding at end of study for clinic appointment attendance with a provider with prescribing privileges
Viral load	PC	x	x	x		We will use standard clinical assays (collected for clinical purposes). An HIV viral load less than 200 will be considered consistent with virologic suppression.

Services Chart Review	PC	x	x	x		PC will use the same Services Tracking Form to capture data on service utilization entered by case managers of SOC and CPT-L participants in the electronic medical record.
Treatment Assessment						
Clinician Survey on PTSD	PC	x	x	x		Assesses therapist experience and attitudes (completed by the project therapist before training, after training, and at 3-month intervals throughout the trial)
Therapist Fidelity Checklist	CM				x	Checklist used by Drs. [name] and [name] in CPT and Lifesteps protocol studies.
Reactions to Treatment						
Client Satisfaction Questionnaire-8	P		x			Likert scale with 8 items that has been standardized to investigate client satisfaction.
Acceptability	P		x			At the first assessment following treatment graduation or discontinuation, participants will complete a survey (1 = strongly disagree to 4 = strongly agree) on their satisfaction (with intervention, therapist, frequency, length of sessions, with amount of confidentiality and respect received); ratings of usefulness of each session; perceived barriers, general experience with the study, likelihood of recommending the study to other patients, and suggestions for improving treatment.
Working Alliance Inventory-Short Revised (WAI-SR)	P		x		x (wk 3; mid treatment)	Assesses three key aspects of the therapeutic alliance: (a) agreement on tasks of therapy, (b) agreement on goals of therapy and (c) development of an affective bond.
Exit Interview	PC		x			Conducted with PC to avoid potential impression management bias. "what are advantages/ disadvantages of getting referred to PTSD treatment, do family members support you, barriers to participation, are there steps in place to help with participation, what were previous barriers to PTSD treatment; would you recommend this to others; how can this intervention better fit your needs, etc."
Summative Exit Interview	AP		x			A research team member will guide CAB members to understand their reactions to the training and treatment models, perceived fit and usefulness within HIV care clinic treatment settings, identified implementation barriers/facilitators, and recommendations to improve larger scale trial procedures

Note. Res = Respondent; P = Participant; CM = Case Manager; PC = Project Coordinator; AP = Advisory Panel; BL = Baseline

\* Collected in Aim 2 participants

† Adherence will be collected up to 6 months after participant completion

**Impact and Future Directions.** Evaluating evidence-based trauma treatments to target specific needs of hard-to-engage populations will significantly impact public health by improving patient outcomes, engagement, and medication adherence across pathologies and health promotion efforts. This study will provide valuable data for PLWH by establishing the protocol for increasing ART adherence and retention in care through an adapted PTSD treatment, CPT-L.

